5.2 Serious Adverse Events (SAEs): Serious adverse events are defined as events

occurring during the clinical trial that necessitate hospitalization, prolong existing hospitalization, result in disability, impair work capacity, are life-threatening or fatal, or cause congenital anomalies.

6. Ethical Considerations

6.1 The clinical study shall be conducted only after the trial protocol has been approved by the Ethics Committee prior to the commencement of the study. The investigator is required to promptly report all changes occurring in the course of the research to the Ethics Committee (including modifications to the protocol and/or informed consent form), and shall not implement such changes without prior approval from the Ethics Committee, unless the changes are necessary to eliminate an apparent and immediate risk to participants. In such circumstances, the Ethics Committee shall be notified.

6.2 Prior to enrollment of each participant, the investigator bears the responsibility of thoroughly informing the participant or their legal guardian of the study's objectives, procedures, potential risks, and information regarding alternative treatments, and of obtaining a signed written informed consent form. Participants shall be informed of their right to withdraw from the study at any time. Informed consent forms shall be retained as clinical research documentation for inspection. Throughout the study, the privacy of participants and the confidentiality of their data will be protected.

7. Data Confidentiality

Results obtained from this study may be published in medical journals; however, patient information shall be maintained in strict confidence in accordance with applicable legal requirements. Personal information of patients shall not be disclosed unless mandated by relevant laws and regulations. When necessary, governmental regulatory authorities, the institutional ethics committee, and their designated personnel may access patient records in accordance with applicable regulations.

8. Anticipated Timeline and Completion Date

The total duration of this project is two years, from March 2026 to March 2028. The planned schedule is as follows:

March 2026 – May 2026: Study preparation.

June 2026 – October 2026: Randomized group allocation of enrolled stroke patients, intervention implementation, and collection of relevant outcome measures.

November 2026 – August 2027: Continued case recruitment, statistical analysis of accumulated data, and objective evaluation of outcome measures across groups.

September 2027 – December 2027: Participation in provincial and national rehabilitation conferences, with preliminary findings presented for peer review and scholarly exchange.

January 2028 – February 2028: Continuation of clinical data collection, synthesis of completed research, comprehensive data analysis, and evaluation of study outcomes.

March 2028: Project completion, manuscript preparation, and publication.

9. Research Team

Name	Title / Specialty	Responsibilities
[name]	Chief Physician	Quality Control
[name]	Chief Physician	Data Analysis
[name]	Associate Chief Physician	Case Recruitment
[name]	Chief Physician	Data Analysis
[name]	Associate Chief Physician	Manuscript Preparation
[name]	Attending Physician	Case Recruitment
[name]	Attending Physician	Case Recruitment
[name]	Attending Physician	Case Recruitment
[name]	Attending Physician	Case Recruitment
[name]	Attending Physician	Rehabilitation Assessment
[name]	Senior Therapist	Rehabilitation Assessment

10. References

- [1] GBD 2021 Causes of Death Collaborators. Global burden of 288 causes of death and life expectancy decomposition in 204 countries and territories and 811 subnational locations, 1990–2021: a systematic analysis for the Global Burden of Disease Study 2021. *Lancet*. 2024;403(10440):2100.

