Treatment Protocol	Neuromodulation Group: Multimodal neuromodulation targeting specific neural regions in addition to conventional therapy. Control Group: Sham stimulation in addition to conventional therapy.
Efficacy Assessment	Primary Outcome Measures: Fugl-Meyer Assessment score; neuroimaging data (cranial CT/MRI); EEG measurements of resting-state and task-state spectral power and functional connectivity; laboratory parameters (complete blood count, CRP, IL-6, S100 β , BDNF). Secondary Outcome Measures: Brunnstrom staging, Modified Ashworth Scale grading, muscle strength, and patient comfort assessment. Safety Assessment Indicators: Complete blood count, blood biochemistry, coagulation function.
Statistical Methods	Key outcome measures will be compared between the neuromodulation group and the control group before and after intervention using independent samples t-tests (two groups) or analysis of variance (multiple groups) to detect statistically significant intergroup differences. Non-parametric tests will be applied to data not conforming to a normal distribution.
Study Duration	March 2026 – March 2028

1. Background and Rationale

According to the World Health Organization (WHO), stroke is the second leading cause of death globally [1]. Approximately 15 million individuals worldwide experience a stroke annually, ranking second only to heart disease, and stroke remains one of the most prevalent causes of long-term disability. Ischemic stroke (IS) constitutes the most common subtype, accounting for approximately 85% of all stroke cases [2]. Among all stroke survivors, over 60% experience varying degrees of functional impairment within three months following the event. The American Stroke Association (ASA) has reported [3] that approximately one-third of stroke patients develop severe speech impairment post-stroke, while one in two patients sustains some degree of hand function loss. Stroke patients frequently contend with chronic functional deficits, including motor difficulties, speech impairment, and cognitive dysfunction, all of which profoundly compromise quality of life. These patients typically require prolonged rehabilitation and nursing care, imposing substantial financial burden on families and exerting considerable pressure on healthcare systems.

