3.2 Sample Size

Participants will be recruited from inpatients of the Department of Rehabilitation Medicine. Based on preliminary literature review and the current inpatient volume of our department, the provisional sample size is set at $n = 60$, with 30 participants allocated to each group.

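### Section 8 schedules between-group outcome evaluation during recruitment and conference presentation before data collection ends, while section 3.2 leaves n = 60 provisional

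*Protocol*

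**What the plan says.** The timeline in protocol section 8 has four entries that bear on this point.

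- June to October 2026: randomisation, intervention and collection of outcomes.
- November 2026 to August 2027: "Continued case recruitment, statistical analysis of accumulated data, and objective evaluation of outcome measures across groups".
- September to December 2027: "Participation in provincial and national rehabilitation conferences, with preliminary findings presented for peer review and scholarly exchange".
- January to February 2028: "Continuation of clinical data collection, synthesis of completed research, comprehensive data analysis, and evaluation of study outcomes".

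On size, section 3.2 reads "Based on preliminary literature review and the current inpatient volume of our department", "the provisional sample size is set at" 60, "with 30 participants allocated to each group". The synopsis and section 3.5.5 give 60 without any qualifier.

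Section 3.7 says that participants do not know their allocation; the protocol says nothing on this for assessors, analysts or recruiters. Section 3.8 places the upper-extremity Fugl-Meyer score, Brunnstrom stage and Modified Ashworth grade among the primary outcomes, assessed immediately after treatment and at 2 weeks. The synopsis describes the tests as meant "to detect statistically significant intergroup differences", without an alpha level or sidedness.

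**The concern.** Read in order, the timeline compares the arms while patients are still being recruited, presents findings in public, collects more clinical data and then analyses again. Two different harms can follow.

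The first is operational. In a single-centre trial with one small team, people who recruit or score later patients can learn which arm is ahead. The Fugl-Meyer, Brunnstrom and Ashworth ratings depend on the rater's judgement, so expectation can move them. Blinding the participant does not prevent this, and a conference presentation removes whatever confidentiality was left.

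The second is inferential. If an early comparison can be reported as the result, or can influence whether enrolment stops or goes on, the overall false-positive rate is no longer the nominal one. Calling the sample size provisional weakens the commitment that would otherwise close off the second route.

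**Working it through.** **Step 1: do the dates fit together?** Inputs: one week for pre-test, five sessions and post-test (section 3.6); outcome assessment up to 2 weeks after treatment (section 3.8); recruitment last named for August 2027 (section 8).

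- Latest named enrolment: 31 August 2027.
- Add 7 days of treatment: 7 September 2027.
- Add 14 days of follow-up: 21 September 2027. A day or two of slack for the post-test still leaves late September.

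The per-participant schedule therefore produces no data in January or February 2028 from anyone enrolled by August 2027. Either enrolment runs past the conference period or the section 8 dates are inconsistent. The document does not say which.

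**Step 2: can the stated sample size be reproduced?** No. Section 3.2 gives no effect size, standard deviation, alpha, power or dropout rate. Its stated basis is the literature and inpatient volume.

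**Step 3: what would repeated looks do to the error rate?** Assumptions, none of them in the protocol: two-sided 0.05 at every look, one endpoint, an approximately normal test statistic, and a significant result at any look counting as a positive trial. The number and timing of looks are not stated, so a range is shown.

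Under the null hypothesis, the statistics at information fractions t_i < t_j have correlation √(t_i/t_j). The overall rate is P(|Z| > 1.96 at one or more looks). For an interim at 50%, the correlation is √0.5 = 0.707.

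| Looks (fraction of 60 patients) | Patients at interim(s) | Chance of any false positive |
|---|---|---|
| 50%, 100% | 30 | 8.3% |
| 70%, 100% | 42 | 7.6% |
| 80%, 100% | 48 | 7.1% |
| 90%, 100% | 54 | 6.5% |
| 33%, 67%, 100% | 20, 40 | 10.7% |
| 50%, 80%, 100% | 30, 48 | just under 9.7% |
| 70%, 90%, 100% | 42, 54 | 8.4% |

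Two looks thus give about 6.5% to 8.3%, and three give about 8.4% to 10.7%. Several co-listed primary outcomes would add further multiplicity that is not counted here.

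**Step 4: when do these figures not apply?** If all 60 patients are completed whatever the looks show, and only the final test is reported as the result, that test keeps its level of 0.05. The operational route does not depend on this condition.

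**The case against.** The best case on the other side has five parts.

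- **The SAP is not at hand.** Interim boundaries, alpha allocation and lock rules are often placed there. This stands: a reader might infer that the trial has no control of repeated looks, but the protocol alone shows only that none is stated in it. No boundary in a SAP, however, can undo public disclosure during data collection or reconcile the section 8 dates.
- **The sample size is largely fixed.** A reader might infer that enrolment will be stopped or extended on seeing results. The documents do not support that. The word provisional appears once, tied to literature and inpatient volume rather than emerging data; the synopsis and section 3.5.5 give 60 outright; and section 6.1 requires ethics approval before protocol changes, except to remove an immediate risk. What remains is an inconsistency that leaves the door open.
- **The 2028 entry does not mention enrolment.** A reader might infer that patients will be treated after the results are public. That is one of two explanations; loosely drafted dates are the other.
- **Entries may be sequential within a window.** Recruitment could finish before the analysis starts within November 2026 to August 2027, and the preliminary findings are not expressly by-arm efficacy results. This is possible, but the entry lists continuing recruitment beside outcome evaluation across groups, and nothing imposes an order.
- **Team roles are separated.** Section 9 lists data analysis, recruitment and assessment on separate rows. That does not amount to restricted access, but it does mean that staff can know the interim results, not that they will.

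**Conclusion.** The point holds as a defect of scheduling and consistency. As written, section 8 provides for between-group outcome evaluation during recruitment and for disclosure before clinical data collection ends. With blinding stated for participants only, this exposes rater-scored outcomes to knowledge of the emerging difference. That bias is real in kind but cannot be sized from the document.

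The inflation of the false-positive rate, to about 6.5% to 8.3% with two looks or 8.4% to 10.7% with three, is conditional. It assumes two-sided 0.05 at each look and requires that a look can support a claim or alter enrolment. It would be wrong to say that the trial's type I error is inflated: the protocol states no such use of interim results, and the final test keeps its level if there is none.

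Correction is warranted before allocation starts in June 2026, because by-arm results cannot be unseen once they have been examined or presented.

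**What to change.** 1. In section 3.2, delete the word provisional so that n = 60 is final and agrees with the synopsis and section 3.5.5.
2. In section 8, limit the November 2026 to August 2027 entry to recruitment, data cleaning and blinded pooled checks.
3. State that no by-arm efficacy analysis or presentation takes place until the last participant's 2-week assessment is entered and the database is locked. Say expressly that safety review is unaffected; section 4.1 names seizure as a risk.
4. Reconcile the recruitment, data-collection and conference dates, with presentation of results after the lock.

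If the sponsor wants an early efficacy result, the alternative is a single pre-specified interim look with adjusted levels, its results kept from recruiters and assessors. To hold overall two-sided 0.05, a Pocock rule needs a nominal 0.0294 at each look for an interim at 50% information, or 0.0347 at 80%. An O'Brien-Fleming-type rule needs 0.0052 then 0.0480 at 50%, or 0.0238 then 0.0432 at 80%.

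The cost is revised wording and a delay of the conference presentation until after the lock. With by-arm efficacy analysis deferred, the single final test keeps the full 0.05.
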